The adenovirus vector ChAdOx1 vaccine technology has been used in the past for the development of candidate vaccines against several infections, including influenza, Zika, and MERS (Antrobus et al, 2014, Folegatti et al, 2020, López-Camacho et al, 2018). Oxford University has adapted and transferred the platform technology used against MERS-CoV to develop a vaccine against SARS-CoV-2, resulting in the rapid development of a vaccine against this infection. The Oxford/AstraZeneca COVID-19 vaccine (AZD1222) is a recombinant replication-defective chimpanzee adenovirus expressing the SARS-CoV-2 S surface glycoprotein (Folegatti et al, 2020). AZD1222 has been shown to be highly efficacious in pivotal randomized clinical trials (RCT), demonstrating 82% overall efficacy against symptomatic infection and 100% efficacy against severe infection. Recent unpublished data from the phase 3 pivotal trial in the United States showed high efficacy (85%) in people 65 years of age or older, and again confirmed 100% efficacy in preventing severe cases. Although a high level of single dose efficacy has been demonstrated in clinical trials between 3 and 12 weeks and confirmed in early effectiveness studies conducted in the United Kingdom (UK), clinical trials and effectiveness study so far have not included detailed vaccine-specific analysis by age group, co-morbidities, nor have they assessed vaccine impact on critical care admission, mortality, and overall outcomes. Similarly, there are few studies taking into account the COVID-19 variant, these data have been aggregated on a national basis by the UK COVID-19 Genomics consortium (UK COG) since September 2020 (Mishra et al, 2021). Thus, it remains important to better understand VE by ages, time intervals between doses, and to determine if single dose effectiveness may extend beyond 12 weeks.

Given mortality due to COVID-19 is highest in long-term care and assisted living facilities and since the Oxford/AstraZeneca vaccine is prioritized for these facilities due to its ease of reach, it is useful to understand the impact of Oxford/AstraZeneca vaccination on hospitalization and mortality for elderly people in these facilities. It's also important to assess VE by age groups and comorbidities for best guidance for COVID-19 immunization programs.

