Summary tables of all patient characteristics and end points indicated in section 9.3.2 will be created for both the before and after matching situation to provide insight in population characteristics as well as in errors and missingness. Categorical variables will be checked on meaningful categories and frequencies. It is not anticipated that categories will have too low frequency. Pooling will be considered when the frequency for a category becomes below 1000.

Continuous variables will be summarized in terms of min, max, interquartile range, median and mean to get insight in these variables, but also to provide a first indication of use of same unit across the database and to obtain a first impression about possible transformations needed. Missing values will be considered in detail. If the percentage of missingness is below 10%, complete case analyses will be performed. When exceeding 10%, multiple imputation will be run additionally based on the total dataset.

For each outcome event, the summary tables will present for each study cohort the number of first events, total person-years for the event and number of first events per person-years (rate), the RR and the VE which is calculated as 1 - RR. This will also be provided per age group and per frailty score where further stratification/subgroups are indicated below. Finally, VE will also be provided in shorter periods after dose 1, and between the doses, and presence of comorbidities.

Poisson regression with offset for time at risk will be used to estimate rates using the matched dataset, adjusting for the matching variables and BMI, smoking, prescribed medications, and frailty score, which are known to increase risk of hospitalization and death and are likely associated with vaccination.

Checks on linearity for continuous variables will be performed. In order to evaluate interactions of independent variables with the exposure (i.e. vaccinated/comparator), continuous variables will be categorized and the VE will be tabulated per category. For variables for which the maximum and minimum VE across categories is more than 10% different, interaction effects with the exposure will be taken into account in the Poisson model. For interactions among independent variables that are not the exposure, interaction variables will be created. Forward selection is performed, and interaction variables will be included when the computed VE changes with more than 10%.

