9.7.2 Stratification/Subgroup Analyses

Stratifications/subgroup analyses will be fully detailed in the SAP, and may include:

- Age: <12, 12-16, 16-49, 50-64, 65-69, 70-79, 80+; or 16-39, 40-<49, 50+, 65+, 80+
- Comorbidity
 - o categories of the CMMS
 - specific comorbidities known to indicate high risk for COVID-19 infections and/or suboptimal response to vaccine, in accordance with National guidance from UK Health Security Agency (UKHSA, 2021) or other, including chronic respiratory disease, chronic kidney disease, chronic heart disease and vascular disease, chronic liver disease, chronic neurological disease, diabetes mellitus, severe mental illness, morbid obesity, asplenia or dysfunction of the spleen, and immunosuppression due to disease or treatment.
- Immunosuppressant prescribed medication: current vs. past use, regimen
- Long-term care or assisted living care residents (if possible)

Stratifications/subgroups in the vaccinated population may include:

- Heterologous dosing
- Vaccine dose: people receiving 1 dose only, ≥1 dose, 2 doses, booster/other additional doses
- Intervals after the 1st dose among people receiving 1 dose only: 0-7, 8-14, 15-21, 22-28, 29-35, 36-42, 43-49, 50-70, 71-77, 78-84 days post dose 1, and/or other combinations may be used
- Interval between doses among people receiving 2 (or more) doses: 21 to 41, 42 to 69, 70 to 77, 78 to 84, over 84 days and/or other combinations may be used.
- Vaccine batch number
- Aged over 65 by electronic frailty index (eFI) categories (mild, moderately, and severely frail)

Stratification/subgroups in the population with COVID-19 may include:

- COVID-19 severity
- COVID-19 variant

Subgroup analyses will only be conducted if sufficient events for an outcome within the subgroup allows.

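### The rule for adding covariate interactions is set on the VE scale, so the rate-ratio shift it tolerates depends on the VE level and is widest for high-VE outcomes

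*Protocol*

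**What the plan says.** Section 9.7.1 of the protocol presents, for each outcome, "the RR and the VE which is calculated as 1 - RR". The model is log-linear in the rate: "Poisson regression with offset for time at risk will be used to estimate rates using the matched dataset". It adjusts for the matching variables plus BMI, smoking, prescribed medications and frailty score.

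Two separate rules for interactions follow. The first concerns interactions with vaccination, which enter the regression under this condition: "For variables for which the maximum and minimum VE across categories is more than 10% different, interaction effects with the exposure will be taken into". The second, at issue here, concerns the other interactions: "For interactions among independent variables that are not the exposure, interaction variables will be created". Selection among these runs forward, and "interaction variables will be included when the computed VE changes with more than 10" per cent. Neither rule says whether 10% is relative or in percentage points. Neither is set on the RR or log-RR scale on which the model is fitted. Both stand in the general methods, so they apply to all outcome models.

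**The concern.** The second rule decides which product terms among covariates are kept for confounding control. A change-in-estimate rule should react to the same amount of confounding in the same way, whatever the vaccine effect. On the VE scale it does not. As VE approaches 100%, a large proportional change in RR (the relative risk remaining after vaccination) becomes a small change in VE.

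The study spans a wide range of VE. The primary outcomes are COVID-19 related hospitalization, ICU admission and death. Section 7 describes the trials as "demonstrating 82% overall efficacy against symptomatic infection and 100% efficacy against severe infection". At the other end are the all-cause outcomes and the early strata in section 9.7.2 ("Intervals after the 1st dose among people receiving 1 dose only: 0-7, 8-14, 15-21"), where low VE is plausible although the protocol gives no figure. Outcomes, periods and subgroups could therefore receive different adjustment sets because their VE differs, not because their confounding differs. The primary objective asks for comparisons across exactly such strata.

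**Working it through.** **Inputs.** VE = 1 − RR and the 10% threshold come from section 9.7.1. VE 82% is the trial figure in section 7. VE 95%, 90%, 50% and 20% are illustrative. The protocol states no derived figure to reproduce.

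**Step 1: largest RR the rule leaves alone when VE falls.** Relative reading: RR′ = 1 − 0.9 × VE. Points reading: RR′ = 1 − VE + 0.10. Fold change = RR′ / (1 − VE).

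| VE | RR | RR′ relative | Fold | RR′ points | Fold |
|---|---|---|---|---|---|
| 95% | 0.05 | 0.145 | 2.9 | 0.15 | 3.0 |
| 90% | 0.10 | 0.19 | 1.9 | 0.20 | 2.0 |
| 82% | 0.18 | 0.262 | 1.46 | 0.28 | 1.56 |
| 50% | 0.50 | 0.55 | 1.10 | 0.60 | 1.20 |
| 20% | 0.80 | 0.82 | 1.025 | 0.90 | 1.125 |

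On both readings the tolerance is widest at high VE. In addition, VE cannot exceed 100%. From a starting VE above 100/1.1 = 90.9% (relative) or 90% (points), no upward change can trigger the rule.

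**Step 2: what the rule does with a 10% or 40% rise in RR.**
- VE 90%: RR 0.10 → 0.11 is VE 89% (1 point, 1.1% relative). RR 0.10 → 0.14 is VE 86% (4 points, 4.4%). Both are ignored on either reading.
- VE 82%: RR 0.18 → 0.198 is VE 80.2% (1.8 points, 2.2%). RR 0.18 → 0.252 is VE 74.8% (7.2 points, 8.8%). Both are ignored.
- VE 20%: RR 0.80 → 0.88 is VE 12% (8 points, 40%), which triggers on the relative reading only. RR 0.80 → 1.12 is VE −12% (32 points, 160%), which triggers on both.

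**Step 3: can an omitted covariate interaction move RR that far?** A Poisson model with main effects only was fitted to expected counts and compared with the model that includes the interaction. Assumptions: two binary covariates, each with rate ratio 1.5, interaction ratio 2 to 5, equal time at risk in both arms.

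- Joint cells balanced between arms, as exact matching gives for the matching variables: no shift at all. The vaccine RR stays at 0.100 or 0.800.
- Both covariates present in 5% of vaccinated and 20% of controls, each alone in 15% of both arms: RR shifts of about 2–5% at VE 90% and 4–8% at VE 20%.
- Each covariate at 30% in both arms, but jointly present in 9% of vaccinated and 20% of controls: shifts of 9–19% at VE 90%.
- The same 30% margins, jointly present in 5% of vaccinated and 25% of controls:

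| Interaction | RR without → with term, VE 90% | VE change | RR without → with term, VE 20% | VE change |
|---|---|---|---|---|
| 2 | 0.085 → 0.100 (×1.18) | 91.5 → 90.0%: 1.5 points, 1.6% | 0.676 → 0.800 (×1.18) | 32.4 → 20.0%: 12.4 points, 38% |
| 5 | 0.071 → 0.100 (×1.41) | 92.9 → 90.0%: 2.9 points, 3.1% | 0.567 → 0.800 (×1.41) | 43.3 → 20.0%: 23.3 points, 54% |

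In the last case the confounding is identical in the two halves of the table. The VE rule keeps the error at VE 90% and removes it at VE 20%, on both readings. A 10% rule on RR acts in all four cells.

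**The case against.** The strongest objection is the matching. Section 9.7.1 matches 1:1 each week on age band, gender, practice or NHS region, and CMMS quartile, exactly if feasible. Section 9.2.4 ends a vaccinated person's follow-up when the matched control is vaccinated. Interactions such as age by CMMS or age by gender are then largely balanced between arms and, as step 3 shows, omitting them does not shift RR. This stands. It does not reach BMI, smoking, prescribed medications and frailty, which are adjusted for but not matched and which the protocol itself regards as likely related to vaccination. Nor does it hold where exact matching fails.

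Second, main effects are in the model regardless, and with moderate imbalance the omitted interaction moves RR by only a few per cent, where a 10% rule on RR would also add nothing. This stands too: the gain appears only under strong joint imbalance. The planned love plots might prompt refined matching, but they compare characteristics one at a time, and in the last scenario each covariate has the same frequency in both arms.

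Third, VE is the reported measure and the SAP may modify the plan. Reporting VE is fine; judging confounding on it makes the tolerance depend on the answer. The SAP can carry the correction, but the protocol already fixes the criterion.

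Fourth, extra terms at low VE do little harm at this sample size. Agreed; the problem is the missing correction at high VE.

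**Conclusion.** The point holds in limited form. The criterion is on the wrong scale and its unit is undefined. On either reading it is loosest at high VE and close to inactive for severe outcomes if their VE is high. RR shifts of 10–40% could be kept there, on the illustrative assumption of strong joint imbalance in unmatched covariates.

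A reader might infer more, which the documents do not support:
- That primary rate ratios could be wrong two- or threefold. The 1.9- to 3.0-fold figures are what the rule would tolerate, and nothing in the protocol suggests that an omitted covariate interaction nearly doubles an adjusted RR.
- That tolerance is nearly zero at low VE. The 2.5% figure needs the relative reading; in points it is 12.5%.
- That the protocol predicts VE of 82–100% for its primary outcomes. Those are trial efficacies cited as background.
- That age-by-comorbidity confounding goes uncontrolled. Matching largely deals with it where exact matching succeeds.

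This is worth correcting because the correction is cheap and can change an adjusted estimate, not because the primary results are shown to be biased.

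**What to change.** In section 9.7.1, apply the 10% change criterion to the adjusted RR for every outcome: include a covariate interaction if |change in ln RR| exceeds 0.095 (ln 1.10 = 0.0953). The trigger is then the same proportional change everywhere and the question of relative or points disappears. A 10% change in RR corresponds to VE 89% or 91% from 90%, 45% or 55% from 50%, and 12% or 28% from 20%.

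Alternatively, drop the selection step and use one common prespecified set of interactions involving the unmatched covariates (BMI, smoking, prescribed medications, frailty) in all outcome models.

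Either change takes one sentence and needs no new data. The downside is a few more model terms, with negligible loss of precision at this sample size.

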9.7.2 Stratification/Subgroup Analyses

Stratifications/subgroup analyses will be fully detailed in the SAP, and may include:

- Age: <12, 12-16, 16-49, 50-64, 65-69, 70-79, 80+; or 16-39, 40-<49, 50+, 65+, 80+
- Comorbidity
 - o categories of the CMMS
 - specific comorbidities known to indicate high risk for COVID-19 infections and/or suboptimal response to vaccine, in accordance with National guidance from UK Health Security Agency (UKHSA, 2021) or other, including chronic respiratory disease, chronic kidney disease, chronic heart disease and vascular disease, chronic liver disease, chronic neurological disease, diabetes mellitus, severe mental illness, morbid obesity, asplenia or dysfunction of the spleen, and immunosuppression due to disease or treatment.
- Immunosuppressant prescribed medication: current vs. past use, regimen
- Long-term care or assisted living care residents (if possible)

Stratifications/subgroups in the vaccinated population may include:

- Heterologous dosing
- Vaccine dose: people receiving 1 dose only, ≥1 dose, 2 doses, booster/other additional doses
- Intervals after the 1st dose among people receiving 1 dose only: 0-7, 8-14, 15-21, 22-28, 29-35, 36-42, 43-49, 50-70, 71-77, 78-84 days post dose 1, and/or other combinations may be used
- Interval between doses among people receiving 2 (or more) doses: 21 to 41, 42 to 69, 70 to 77, 78 to 84, over 84 days and/or other combinations may be used.
- Vaccine batch number
- Aged over 65 by electronic frailty index (eFI) categories (mild, moderately, and severely frail)

Stratification/subgroups in the population with COVID-19 may include:

- COVID-19 severity
- COVID-19 variant

Subgroup analyses will only be conducted if sufficient events for an outcome within the subgroup allows.

9.7.3 Sensitivity Analyses

Several sensitivity analyses will be considered

- Only HES data are included for follow-up data on hospitalization and ICU-admission
- People with history of COVID-19 infection prior to vaccination not excluded from the study population
- A COVID-related event within 14 days of a positive RT-PCR for SARS-CoV-2 infection.
- Addition of the following exclusion criterion: People whose household had more than 10 people with an average age of 65 years and over. This is a proxy for people living in an elderly care home (and only available for a subset of ORCHID data). They will generate a strong confounding effect of (due to the targeted vaccination of these residents and their high risks of COVID-19-related events) and the lack of available controls.

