9.2.3 Exclusion Criteria

People who meet the following criteria will be excluded:

• Primary analysis: People with a history of COVID-19 infection (confirmed by reverse transcriptase polymerase chain reaction (RT-PCR) or not) prior to vaccination. This group of people is not excluded in the sensitivity analysis.

A sensitivity analysis excluding persons living in an elderly care home will be considered.

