9.2.4 Participant Follow-up

For the vaccinated and concurrent control arms, study participants will be followed from the index date to the end of the study, loss to follow-up (deregistration), vaccination (for unvaccinated controls), vaccination of the matched control (for vaccinated people), or death, whichever is earlier.

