9.3.2 Outcomes

The primary outcomes of this study are

- COVID-19 related hospitalization
- COVID-19 related ICU admission
- COVID-19 related death

The secondary outcomes of this study are

- All-cause hospitalization
- All-cause ICU admission
- All-cause mortality

The RAVEN extension outcomes are:

- Any positive SARS-CoV-2 test
- Medically attended COVID-19
- Emergency department visit associated with COVID-19
- HCRU (including but not limited, primary care consultations, prescriptions, medical tests and investigations; hospital outpatient attendances and procedures; hospital emergency department attendances without admission; hospital admissions) and associated cost related to COVID-19 and long COVID
- Breakthrough case
- Time to vaccine waning
- Long COVID (e.g. based on code for long COVID, on combination of code for long COVID and a positive SARS-CoV-2 test, on referral to long COVID clinic)
- A COVID-19 related event (GP attendance, accident department, hospitalization, ICU admission, death) is defined as:

- A medically attended event "Acute symptomatic COVID" defined as a positive test plus a clinical diagnosis or symptom (e.g. anosmia) which makes COVID plausible
- An emergency department attendance
- An event with an ICD-10 diagnosis of COVID-19
- An event within 28 days of a positive RT-PCR for SARS-CoV-2 infection or
- A visit with a patient presenting with respiratory symptoms or other symptoms credibly associated with COVID-19 within 28 days of a positive RT-PCR for SARS-CoV-2 infection.
 - Events within 14 days will feature in a sensitivity analysis.

Events of interest are those occurring between the index date and the end of follow-up. Only the first outcome event will be considered in the primary and secondary VE analysis.

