The Hospital Episode Statistics (HES), Secondary Uses Service (SUS), General Practice Extraction Service data for pandemic planning and research (GDPPR), and Office of National Statistics (ONS) data may include information on COVID-19 infection through specific COVID-19 diagnosis codes. Using a combination of both COVID-19 SGSS/NPEX and diagnosis codes from HES, SUS, GDPPR, and ONS allow capturing the COVID-19 infection status for all study participants. Since testing for COVID-19 and its capture was not complete at the beginning of the pandemic but significantly improved later, restriction of the study period from July 2020 or the 2nd wave of infection by regions in England, whichever is later, for determining COVID-19 related events in the historical population is needed. Medically attended COVID-19 will come from ORCHID, GDPPR, Emergency Care Data Set (ECDS) and HES. Emergency department visits will come from ECDS. SARS-CoV-2 variants will come from COG UK. Data on HCRU and associated cost will come from HES using the Health Resource Grouper (HRG) and primary care attendance and medication costs. Long COVID will come from ORCHID and HES.

|--|

Variables		Data source	Comments
Hospitalization	Date	HES for curated data	6-8 weeks lag for HES
	Frequency	SUS for more recent raw data	SUS is updated weekly
	Duration	HES APC for combined	with a maximum of 2 weeks lag
ICU admission	Date	CC for ICU specific data	
	Frequency		
	Duration		
Death	Date	ORCHID/GDPPR for date	2 weeks lag
	Cause of death	ONS for cause of death	6 weeks lag
Medically attended COVID-19		ORCHID, GDPPR, ECDS, HES	
COVID-19 infection	Positive RT-PCR test; date	SGSS for first positive test in hospital and community NPEX for all positive/negative test in the community	Daily update
	ICD-10/SNOMED codes for COVID	HES, ONS, GDPPR	
SARS-CoV-2 variants of interest		COG UK	
Long COVID		ORCHID, HES	
HCRU and cost		HES & HRG	
		ICU datasets	
		Primary care attendance & costs	

APC: Admitted Patient Care; CC: Critical Care COG UK: COVID Genomics UK Consortium; ECDS: Emergency Care Data Set; GDPPR: General Practice Extraction Service data for pandemic planning and research; HES: Hospital Episode Statistics; HRG: Health Resource Grouper; ICU: Intensive Care Unit; NPEX: National Pathology Exchange; ONS: Office for National Statistics; ORCHID: Oxford-Royal College of General Practitioners Clinical Informatics Digital Hub; SGSS: COVID-19 Second Generation Surveillance System; SUS: Secondary Uses Service.

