- Civil Registrations (Deaths): Information including the date, place and certificated cause of death from the Office for National Statistics (ONS) (Time lag 8-12 weeks, released by NHS Digital with HES)
- COVID-19 SGSS Demographic and diagnostic information from laboratory test reports for patients tested for COVID-19 in England only. It currently includes the first positive results from pillar 1 (swab testing in Public Health England (PHE) and NHS hospital labs and pillar 2 (swab testing for the wider population) (Time lag less than 1 week)
- COVID-19 UK Non-hospital Antigen Testing Results (Pillar 2) data includes a range of COVID19 test results, including NPEX. This is broadly similar to SGSS, but only covers Pillar 2 data, however, contains the full result set i.e. all positive, negative and null results.
- COVID-19 Hospitalization in England Surveillance System (COVID-19 SARI-Watch/CHESS): Epidemiological data on COVID-19 infection in persons requiring hospitalization in ICU or High Dependency Units. It records all demographic, risk factor, treatment and outcome information for patients admitted to hospital with a confirmed COVID-19 diagnosis. This only has data from a limited number of surveillance hospitals. (Time lag – less than 1 week)
- SUS Episodes (including the following concepts: Admitted Patient Care (APC), Outpatient, Critical Care & A&E). This covers all secondary care provided in England and paid for by the NHS. This is essentially the CDS. These data are transformed to create HES product set that is subject to official publication timelines. Therefore, SUS should be considered tactical but carries a shorter latency (Time lag –1-2 weeks). Only available for linkage to ORCIHD.

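### When previously infected people are admitted to the sensitivity analysis, a positive test in the 28 days before index can make an infection that began before time zero count as a COVID-19 outcome

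*Protocol*

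**What the plan says.** Protocol 9.2.3 excludes people with a history of COVID-19 infection from the primary analysis and adds: "This group of people is not excluded in the sensitivity analysis". Section 9.7.3 lists the corresponding analysis as "People with history of COVID-19 infection prior to vaccination not excluded from the study population". Neither section states how long ago the infection must have been.

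On timing, 9.2.4 says that "study participants will be followed from the index date to the end of the study", subject to the usual censoring. Section 9.3.2 says "Events of interest are those occurring between the index date and the end of follow-up". One of the routes by which an event counts as COVID-19 related is "An event within 28 days of a positive RT-PCR for SARS-CoV-2 infection or" one of the other listed routes. A diagnosis code for COVID-19 is another route and needs no test. A shorter window is a separate item in 9.7.3: "A COVID-related event within 14 days of a positive RT-PCR for SARS-CoV-2 infection".

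On test sources, the outcome table in 9.3.2 gives "SGSS for first positive test in hospital and community", with NPEX supplying all results from the community. Section 9.4 agrees about SGSS: "It currently includes the first positive results from pillar 1" and from pillar 2.

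**The concern.** The start-of-counting rule restricts the date of the event. Nothing restricts the date of the test that labels it as COVID-19. In the primary analysis this does no harm, because someone known to be positive before index is excluded. Once the exclusion is lifted, a person who tests positive on day -5 and is admitted on day +6 becomes an outcome, although the infection preceded vaccination or selection as a control.

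What is at stake is the reading of this analysis. It is there to show whether the primary VE depends on excluding prior infection. Section 9.9 already warns that it drifts towards comparing two immune states and expects VE to fall over time. It does not mention carry-over. If carry-over is equal in the two arms it imitates such a fall; if it sits mainly in controls it hides one. A gap between this analysis and the primary one could then not be attributed to natural immunity.

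**Working it through.** The plan gives no figure on this point to reproduce, so the check is date arithmetic followed by an illustration.

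**Window.** Inputs: look-back of 28 days, or 14 in the variant (9.3.2, 9.7.3); counting from day 0 (9.2.4, 9.3.2); index is the first-dose date (9.2.1). An event on day e ≥ 0 qualifies through a PCR on any day from e - 28 to e. It is carried over if that PCR day is below 0.

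- The last affected event day is 28 - 1 = 27, so the affected event days are 0 to 27 and the test days are -28 to -1.
- With the 14-day window, the affected event days are 0 to 13.
- A positive on day -k can qualify events on days 0 to 28 - k, which is 29 - k days: 28 days for k = 1, but only one day for k = 28.

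**Which estimates are affected.**

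| Estimate | Carry-over through the PCR route |
|---|---|
| Counted from index (at least one dose, overall) | event days 0-27 |
| Post-dose strata 0-7, 8-14, 15-21 days (9.7.2) | all days |
| One-dose status, from day 22 (9.3.1) | event days 22-27, test days -6 to -1; nil with the 14-day window |
| Two-dose status | nil: shortest listed interval 21 + 15 = day 36, beyond day 27 |
| Primary analysis; all-cause outcomes | none |

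The first row takes 9.2.4 and 9.3.2 as written. If the day-22 rule were also applied to the at-least-one-dose estimate, only days 22-27 would remain there.

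**Effect on VE.** Let c be carry-over events in controls divided by genuine control events, and r the ratio of vaccinated to control carry-over. Then

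observed VE = 1 - [(1 - VE) + r·c] / (1 + c).

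The documents supply none of these inputs. Assume VE = 60%, a genuine control incidence of 0.1%, 0.5%, 1% or 2% of controls positive in the 28 days before index, and 3% of those having a qualifying admission. Then c = 0.005 × 0.03 / 0.001 = 0.15, and likewise 0.30 and 0.60.

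| r | c = 0.15 | c = 0.30 | c = 0.60 |
|---|---|---|---|
| 0.1 | 64% | 67% | 71% |
| 0.4 | 60% | 60% | 60% |
| 1.0 | 52% | 46% | 38% |

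For example, with r = 0.1 and c = 0.15: 1 - 0.415/1.15 = 64%. With r = 1 and c = 0.15: 1 - 0.55/1.15 = 52%. The bias vanishes when r = 1 - VE, here 0.4, and changes sign above that.

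With smaller carry-over and an assumed VE of 80%:

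- 10% in both arms gives 1 - 0.30/1.10 = 72.7%.
- 10% in vaccinated only gives 1 - 0.30/1.00 = 70.0%.
- 10% in controls only gives 1 - 0.20/1.10 = 81.8%.

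**Test capture at reinfection.** SGSS holds first positives only and NPEX holds all results for the community only. A previously infected person who is retested only in hospital leaves no new qualifying PCR. The event can still be found through a diagnosis code, since 9.3.2 accepts an ICD-10 code alone and combines tests with codes from HES, SUS, GDPPR and ONS.

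**The case against.** The strongest reply is that the checklist in Appendix B leaves outcome definition and measurement to the SAP, and that 9.7.3 gives one line to each analysis that will be considered. A washout may well be specified there. This stands as far as a bare omission goes. It does not answer the rule that 9.3.2 itself states: a 28-day look-back, counting from index, and no condition on the test date. Followed as written, that rule gives the wrong result in this population.

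The second reply is that the exposure lags and the 14-day analysis shrink the problem. They do. Carry-over all but disappears from dose-specific status. It remains in index-based estimates and early strata, and the 14-day variant is a separate analysis that would still leave days 0-13 exposed.

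Three stronger readings are tempting, and the documents do not support them:

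- **That VE is inflated.** This needs recent positives to be concentrated in controls, for instance because infected people defer vaccination. The protocol gives no such rates, and equal carry-over pulls VE towards zero.
- **That hospital-tested reinfections are missed.** The diagnosis-code route covers coded events, and NPEX covers community tests. What is lost is hospital-tested but uncoded reinfections, together with outcomes that depend on a test.
- **That the analysis should therefore move to an ICD-10-only outcome.** That would change population and outcome definition together and spoil the comparison with the primary analysis.

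**Conclusion.** The point holds for the sensitivity analysis that keeps previously infected people. As the rules stand, infections already test-positive up to 28 days before index can be counted as COVID-19 hospitalizations, ICU admissions or deaths on days 0 to 27. The date arithmetic rests only on the protocol's own rules.

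Size and direction are not established. The illustrated range, from 38% to 71% around a true 60%, rests wholly on assumed incidence, recent-positive share, admission risk and arm ratio. It shows that the sign turns on the arm ratio; it does not predict the bias. The 3% is also a single average over days -28 to -1, although positives further from index have fewer event days in which to qualify. Carry-over ends at day 27, so its share shrinks as follow-up lengthens.

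The primary VE result is not in question. The change is worth making because it is cheap and because without it this analysis cannot be read clearly against the primary one. First-positive-only capture in SGSS is a secondary caveat to report.

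**What to change.** In 9.7.3, exclude from both arms anyone with a positive test or a COVID-19 diagnosis in the 28 days before the index date, and admit only earlier infections. In 9.3.2, require a qualifying positive test to be dated on or after the index date. Together these cut the PCR-route window from 28 event days to none. The washout is the essential part: an admission after index for an infection before index can carry a COVID-19 code of its own, and a test-date rule alone would not remove it.

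Keep the same outcome definition as in the primary analysis. State that hospital-tested reinfections are found only through diagnosis codes, and that test-based outcomes in previously infected people are under-ascertained to that extent.

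The cost is two sentences and one date filter on data already held. The downside is that a few recently infected people are dropped from this one sensitivity analysis.
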